## 1. BACKGROUND

Cataracts are the most common cause of low vision and blindness in the world (Brian and Taylor, 2001). Cataracts occur when the crystalline lens becomes cloudy preventing light from reaching the retina and so resulting in poor vision. Cataract is highly treatable and the surgery involves removing the cloudy crystalline lens and replacing it with a clear artificial plastic lens (made of acrylic) called an Intraocular lens (IOLs) (Foster, 2001).

Around one fifth of people attending for cataract surgery have astigmatism (Swampillai *et al.*, 2020). Astigmatism refers to the imperfection in the curvature of the cornea, the clear and dome-shaped covering in front of the eye. An eye with severe astigmatism is oval (like a rugby ball) instead of round like a football. This oval shape reduces vision and make vision blurry all over, not just close-up, or far away. While most astigmatism orientated with the steep curve vertically, for some, it can be horizontal (the rugby ball on its side) or more rarely, obliquely positioned (neither horizontal nor vertical). Degree of astigmatism is measured in dioptre (D). A perfect eye has zero dioptre. Most people can have between 0.5-0.75 D and people with 1.5D or more typically need to wear contact lenses or eyeglasses for clear vision.

Conventional non-Toric monofocal IOLs is the most common implants used in cataract replacement surgery. They stay focused at one fixed distance and when chosen to correct distance vision error such as short-sightedness, reading glasses may be needed to see thing close-up. Also, these lenses do not correct astigmatism. In most NHS hospitals such as in UHP, astigmatism often is left untreated during the cataract replacement surgery.

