### 6.1 Inclusion criteria

- Participants capable of giving informed consent
- Age 50 years or above
- Diagnosed with bilateral cataract with corneal astigmatism 1.00D or above
- Previously consented to routine NHS cataract surgery

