### 6.2 Exclusion criteria

- Irregular astigmatism, Amblyopia

Vision and balance changes after bilateral implantation of Toric IOLs  
IRAS ID: 286913

- Any pre-surgical corneal complications or pathology such as Fuchs dystrophy, keratoconus
- Macular pathology, glaucoma, retinal disease, abnormal iris or pupil deformation
- Irregular or malformed eyelids such as ptosis, chalazion or severe blepharitis
- Previous corneal or intraocular surgery
- Any patient who does not have traditional phacoemulsification extraction will be excluded from the remainder of the study
- Incapable of giving informed consent due to lack of mental capacity, problems with communication or language and any conditions preventing the patient from fully understanding the procedures and nature of the study
- Predicted bilateral post-op corneal astigmatism of  $<1.50D$ , dilated pupil size smaller than 5mm
- Unable to walk independently with or without walking aids for 10 meters

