### **10.3 Statistical analysis plan**

All data will be assessed for normality using a combination of assessing histogram plots and the Shapiro-Wilks Normality Test. Descriptive summary statistics for outcome measures relating to vision (acuity and refraction) will be recorded as mean +/- standard deviation.

Mixed ANOVA and post-hoc Bonferroni tests will be used to determine the statistical differences in the baseline characteristics and outcome measures between the Toric monofocal IOLs group and the non-Toric monofocal IOLs group. The between-subjects factor would be type of IOL lens and the within-subjects factor would be time (pre-surgery vs post-surgery). Level of significance will be set at 0.05.

Vision and balance changes after bilateral implantation of Toric IOLs  
IRAS ID: 286913

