### 10.3.1 Summary of baseline data and flow of patients

[figure not shown]
Randomization	Sample size calculation with the G* Power 3 program N=140	Randomization list generated in MS Excel at the commencement of the study by the Chief investigator: independent of assessment and intervention	Execution- randomization list will be held by the PI (ophthalmologist at REI) so that they know who is allocated into either the intervention or control groups according to the list.
Outcome measures		Trial description	Outcome recorded
Primary outcomes Dynamic stability	1.Eye gazing characteristics	Gazing duration on obstacles during the obstacle negotiation.  Area of interest and corresponding glazing duration during stair walking	
 
Gazing duration and frequency on obstacles and area of interest.
 
Heat map on area of interest from eye tacking device
 
 
all data will be recorded and saved in file name in the format: participant number-obstacle-trial1/2/3-date.

	2.Movement biomechanics	
-participants perform Timed up and go (TU&G) test involving getting up from chair ,then walking over 3m level ground, turning and walking back to sit down on the chair
 
- participants walk over a 3m level ground with obstacles of different contrast colour to background.
 
- accelerometers of head tilting and change in movement of centre of gravity will be recorded during TU&G test and during crossing over obstacles.
	
 
accelerometers data of change in head tilting and centre of gravity will be recorded
 
Duration in seconds of TU&G test
 
 
all data will be recorded and saved in file name in the format: participant number-obstacle-trial1/2/3-date.

Secondary outcomes	1.Refraction and visual acuity	-standardized protocol for routine visual function test	-vision 20/20, sphere cylinder, axis -DVA, NVA -IOL rotation (for Toric IOL group only)
	2.Questionnaire	Short Fall Efficacy Scale International Fear of Falling Questionnaire CAT-PROM 5 Quality of life Questionnaire	

- A CRF form has been prepared for this study

Vision and balance changes after bilateral implantation of Toric IOLs  
IRAS ID: 286913

**Modified CONSORT flow diagram  
for**

**Vision and balance changes using after bilateral  
implantation of Toric versus non-Toric intraocular lenses in  

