### 10.3.3 Secondary outcome analysis

Outcomes	Data collected	Data type	Quantitative statistical Analysis
Eye glazing characteristics during obstacle crossing and stair walking	Gazing duration on obstacles and area of interest on environment during stair walking  Area of interest determined by heat map (area with highest frequency of gazing)	Interval  Gaze pattern of location of hotspots and duration of gaze will be collected using Tobii pro eye tracker.  % time spent on fixation of highlighted object or area of interest  Best performance among 3 trials will be used.	Mixed ANOVA and post-hoc Bonferroni tests will be used to determine the differences between the Toric IOLs group and Monofocal IOLs group before surgery and 6 months after second eye surgery.
Refraction and visual acuity	-Visual acuity (vision, sphere, Cylinder, Axis, DVA, Add NVA) -IOL tilt and decentration -IOL rotation (for Toric IOL group only)	Interval  Average tilt, decentration and rotation of lens will be analysed by calculating average value in Toric and monofocal groups. Bland Altman will be used to study the agreement of position-level of error for IOLs tilt, decentration and rotation.	Mixed ANOVA and post-hoc Bonferroni tests will be used to determine the differences between the Toric IOLs group and Monofocal IOLs group before surgery and 6 months after second eye surgery.  Unaided and aided distance visual acuity will be recorded in Log MAR and comparisons between the two lenses pre and post cataract surgery will be conducted using a two-way ANOVA. Post-operative refractive astigmatism will be analysed using the Alpins method*. Correlation between SIA and TIA will be assessed, and dependent t-tests will be used to analyse the remaining metrics in the two groups
Questionnaire	Short Fall Efficacy Scale International	Ordinal (non-parametric)	Mixed ANOVA and post-hoc Bonferroni tests will be used to determine the differences between the Toric IOLs group

Vision and balance changes after bilateral implantation of Toric IOLs  
IRAS ID: 286913

	Fear of Falling Questionnaire CAT-PROM 5 Quality of life Questionnaire		and Monofocal IOLs group before surgery and 6 months after second eye surgery.
--	---	--	--

\*Post-operative refractive astigmatism will be analysed using the Alpíns method. Cylindrical power and axis will be converted to vectors (J0 and J45; Equations 1 & 2).

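### Raw sphere is listed as a refraction outcome and appears to fall under the between-arm ANOVA, but it carries half the residual cylinder, so it should be replaced by spherical equivalent

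*Combined protocol and SAP*

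**What the plan says.** Section 10.3.3 has a row for refraction and visual acuity. Its data-collected cell contains "Visual acuity (vision, sphere, Cylinder, Axis, DVA, Add NVA"), its data type is interval, and its analysis cell opens with "Mixed ANOVA and post-hoc Bonferroni tests will be used to determine the differences between the Toric IOLs group and Monofocal IOLs group". The same cell then gives specific methods for logMAR distance acuity (two-way ANOVA) and for refractive astigmatism (Alpins method). No other method in the row could apply to sphere.

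Two other places treat sphere as an outcome. The table in 10.3.1 lists "vision 20/20, sphere cylinder, axis" in its column of recorded outcomes. Section 10.3 says: "Descriptive summary statistics for outcome measures relating to vision (acuity and refraction) will be recorded as mean +/- standard deviation".

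The astigmatic part is handled separately: "Cylindrical power and axis will be converted to vectors (J0 and J45; Equations 1 & 2"). The third component of that decomposition, spherical equivalent, is not mentioned anywhere in the supplied text. Nor is a plus- or minus-cylinder convention, or a target refraction.

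On the control lens, section 1 states: "Also, these lenses do not correct astigmatism". Section 6.1 admits patients "Diagnosed with bilateral cataract with corneal astigmatism 1.00D or above". Section 6.2 excludes those with "Predicted bilateral post-op corneal astigmatism of" less than 1.50 D.

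**The concern.** Sphere is not a free-standing measure of spherical correction. The number written down depends on how much cylinder the eye has and on which of two equivalent notations the examiner uses. In most trials this averages out between arms. Here the arms are meant to differ in residual cylinder, because correcting it is what the Toric lens does.

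Two lenses with identical spherical results would therefore show different mean sphere. In minus-cylinder form the non-Toric arm would look more hyperopic; in plus-cylinder form it would look more myopic. A reader could take this as a second, spherical difference between the lenses, when it is the astigmatism result counted again. If notation varied between examiners or visits, the average would have no clear meaning.

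**Working it through.** **The plan's own figure.** The documents give no figure for sphere. The number carried forward is 55 evaluable per arm (10.1). For the between-groups test of a repeated-measures ANOVA with f = 0.25, α = 0.05, two groups, two time points and an assumed within-person correlation of 0.5 (not stated in the documents), the noncentrality at N = 110 is 0.25² × 110 × 2 / (1 + 0.5) = 9.17. Power is 85.1%, so 55 per arm reproduces. For dropout, 55 / 0.8 = 68.75, or 69 per arm, against 70 planned.

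**The identity.** With S = sphere, C = signed cylinder and SE = S + C/2:
- minus-cylinder form: S = SE + |C|/2
- plus-cylinder form: S = SE − |C|/2

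Example: +0.75/−1.50 and −0.75/+1.50 are the same refraction. SE is 0.75 − 0.75 = 0 in the first form and −0.75 + 0.75 = 0 in the second, yet sphere differs by 1.50 D.

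**Shift between arms if mean SE is equal.** The non-Toric minus Toric difference in mean sphere is ±(mean |C| non-Toric − mean |C| Toric)/2. Residual cylinders are assumed.

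| Residual cylinder, non-Toric vs Toric | Shift in mean sphere |
|---|---|
| 1.0 vs 0.5 D | ±0.25 D |
| 1.5 vs 0.5 D | ±0.50 D |
| 2.0 vs 0.5 D | ±0.75 D |

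**Chance of a significant post-operative contrast.** Further assumptions:
- one refraction value per participant, 55 per arm
- SD of SE 0.5 or 0.8 D, and SD of cylinder 0.5 D, independent of SE
- Bonferroni for two contrasts (before and after surgery), so two-sided α = 0.025

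The SD of sphere is √(0.5² + 0.25²) = 0.559 D or √(0.8² + 0.25²) = 0.838 D. The noncentrality is shift/SD × √(55/2), with 108 degrees of freedom.

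| Shift | SD of sphere | Noncentrality | Chance of significance |
|---|---|---|---|
| 0.25 D | 0.559 | 2.35 | 53% |
| 0.25 D | 0.838 | 1.56 | 24% |
| 0.50 D | 0.559 | 4.69 | 99% |
| 0.50 D | 0.838 | 3.13 | 80% |

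**Arm-by-time interaction.** With two time points this is a t-test on change, here at α = 0.05. Pre-operative sphere is assumed independent of post-operative sphere, so the SD of change is √(pre-operative SD² + post-operative SD²). For the 0.25 D shift the chance is about 8% if pre-operative sphere has an SD of 2.5 D, and 17-21% if the SD is 1.0 D. For the 0.50 D shift it is about 17% and 51-62%. All are below the corresponding post-operative contrast.

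**Control.** In 4,000 simulated trials per setting with equal SE in both arms, an unadjusted 5% test on SE rejected in 4.5-5.7%, as it should. Raw sphere at 1.5 vs 0.5 D (SD of SE 0.5-0.75 D) rejected in 91% to nearly 100%, with mean differences of about +0.49 D in minus-cylinder and −0.49 D in plus-cylinder form. These are slightly under 0.50 D because simulated cylinder was cut off at zero.

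**The case against.** **The plan may not intend to test sphere.** The ANOVA sentence names no variable. It cannot cover everything in its cell, because IOL rotation is recorded for the Toric group only. Sphere, cylinder and axis are also simply how a refraction is written down. This stands in part: the text is ambiguous. But sphere is also listed as a recorded outcome in 10.3.1, 10.3 calls for a mean and SD of refraction, and no other method is offered for it. An analyst following the text would reach the ANOVA, and a table of mean sphere by arm would mislead even without a test.

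**Spherical accuracy is not an endpoint.** Sections 3.2, 3.5 and 3.6 do not name it. This stands. A reader might infer that the plan lacks a valid comparison of spherical accuracy, but it never promises one, and no passage says that a sphere difference will be interpreted that way.

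**A false difference requires equal SE targets.** This stands as an assumption; the documents state no target. A difference in recorded sphere would be a real difference in the recorded numbers. Reading it as spherical performance would be the error.

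**The size depends on the residuals chosen.** This stands. A reader might infer that a significant result is almost certain, but that needs a non-Toric residual of about 1.5 D or more. Section 6.1 admits 1.00 D, section 10.4 plans a subgroup below 1.50 D, and the 1.50 D bound in 6.2 concerns corneal rather than refractive cylinder.

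**Notation may be fixed elsewhere**, in the case report form or the visual function test protocol. Neither is in the supplied text. Fixing notation would settle the sign but leave the shift.

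**Conclusion.** The point holds as a minor one. Raw sphere is listed as an interval outcome, the row's mixed ANOVA is the only between-arm method that could apply to it, and SE is absent. If both arms share the same SE target, mean sphere will differ by half the difference in residual cylinder, in a direction set by notation. The identity is exact; the sizes rest on assumed residuals and SDs: about 0.25 D and 24-53% significance at 1.0 vs 0.5 D, and about 0.50 D and 80-99% at 1.5 vs 0.5 D, for the adjusted post-operative contrast.

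Only a secondary refraction result is affected. The documents do not support extending the point to the primary outcome, the sample size or the secondary endpoints named in 3.5; none of these uses sphere.

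**What to change.** In 10.3, 10.3.1 and 10.3.3:

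1. Use spherical equivalent (sphere + cylinder/2) in place of raw sphere for between-arm summaries and tests.
2. State one cylinder notation for all visits and examiners.
3. Leave the astigmatic part to the J0/J45 analysis already planned.
4. Keep raw sphere as recorded data, with no between-arm comparison.
5. Say which variables in the refraction row the mixed ANOVA covers.

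This is a wording change. SE is calculated from sphere and cylinder, both already listed for collection, so no new measurement is needed.

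Deviation from intended SE could be added, but it is optional. It would be a new analysis, and it needs the target refraction, which the plan does not list and which would have to be retrieved from the lens-power planning record (lens power is calculated under 8.5).

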## **10. STATISTICS AND DATA ANALYSIS**

### **10.1 Sample size calculation**

Sample size test calculation was carried out with the G\*Power 3.1 program (Faul *et al.*, 2007) for comparison of the main outcome measure of dynamic balance (between IOL design) using mixed ANOVA (repeated measures, between factor being the type of IOL).

Based on of the dynamic balance measurement (JERK score) in a previous study (Mancini *et al.*, 2011) an estimated medium effect size (0.25) will be used. With a power of 85% and level of significance ( $p$ ) set at 0.05 and effect size of 0.25, 55 participants will be required in each group (Monofocal vs Toric IOL). Accounting for a 20% drop out rate, 70 participants will therefore be recruited in each group (A total of 140 participants).

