## 16.2 Appendix 2 - Schedule of Procedures

Procedures	Visits x3					
	Screening	Baseline (study visit 1)	Treatment Phase (routine cataract surgery schedule and care)		Follow Up after 1 st eye surgery (study visit 2)	Follow Up after 2 nd eye surgery (study visit 3)
Informed consent	x	x				
Demographics		x				
Medical history	x	x				
General eye examination		x			x	x
Visual function -visual acuity -astigmatism power	x	x			x	x
Eligibility assessment	x					
Randomisation	x	x				
Dispensing of Toric and Monofocal IOLs		x	x	x		
Compliance (IOLs post-op care)			x	x		
Dynamic stability assessment 1. Motion sensor and eye tracking during Timed up & go test (TUG)		x			x	x
Dynamic stability assessment 2. Motion sensor and eye tracking during walking over obstacles		x			x	x
Dynamic stability assessment 3. Motion sensor and eye tracking during stair walking		x			x	x
Risk of fall Questionnaires -Short Fall Efficacy Scale -Fear of falling		x			x	x
Quality of life questionnaire -CAT-PROM5		x			x	x
IOL orientation (Toric IOL only)		x			x	x

Vision and balance changes after bilateral implantation of Toric IOLs  
IRAS ID: 286913

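### The vision row of the analysis plan names two tests for acuity, states no unit of analysis for two-eye data, and assigns lens position a pre/post between-arm ANOVA that it cannot support

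*Combined protocol and SAP*

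**What the plan says.** Section 10.3 sets the general rule, a mixed ANOVA with Bonferroni post-hoc tests: "The between-subjects factor would be type of IOL lens" and "the within-subjects factor would be time (pre-surgery vs post-surgery"). It adds: "Level of significance will be set at 0.05". Section 10.1 sizes the trial on the same family: "mixed ANOVA (repeated measures, between factor being the type of IOL").

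In the table in section 10.3.3, the analysis cell for refraction and visual acuity opens with the sentence used in every row: "Mixed ANOVA and post-hoc Bonferroni tests will be used to determine the differences between the Toric IOLs group and Monofocal IOLs group before surgery" and six months after the second eye. The cell then gives aided and unaided LogMAR distance acuity a sentence of its own: "comparisons between the two lenses pre and post cataract surgery will be conducted using a two-way ANOVA". That sentence names no repeated factor and no participant term.

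The same row contains tilt, decentration and "IOL rotation (for Toric IOL group only"). Its data-type column gives these three measures arm averages, for the Toric and the monofocal group alike, and a Bland-Altman analysis. Appendix 2 has a row labelled "IOL orientation (Toric IOL only"), marked at baseline and at study visits 2 and 3.

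Section 8.6 has each eye implanted on a separate occasion, and section 7.3 allocates lens type by participant. The plan does not say whether acuity, refraction or lens position is analysed per eye, per participant or binocularly.

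**The concern.** An analyst working from this row has three questions that the text does not settle.

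- **Which test applies to acuity?** Two names are given. If they mean different models, one of them could treat a person's pre- and post-operative readings as unrelated, and the choice could be made after seeing results.
- **What is the unit?** Each participant contributes two eyes with the same lens type. Entering both as separate, independent records would overstate the information in the trial.
- **What is to be done with lens position?** The row-level sentence asks for a pre/post comparison between arms. An implanted lens has no position before surgery, and rotation is recorded in one arm only.

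Visual function and lens orientation are named secondary objectives (section 3.2), so these results will be reported and interpreted.

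**Working it through.** **Inputs from the documents.** 55 evaluable participants per arm, effect size 0.25, power 85%, alpha 0.05, 20% dropout, 70 recruited per arm (section 10.1). Two operated eyes per participant (section 8.6).

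**Assumptions.** The documents give no pre/post correlation ρ and no inter-eye correlation. Ranges used: 0.3 to 0.7 and 0.3 to 0.9.

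**The plan's own figure.** For a between-factor repeated-measures ANOVA, λ = f²·N·m / (1 + (m − 1)ρ), with 1 and N − 2 degrees of freedom. With m = 2 time points and ρ = 0.5 (neither is stated), λ = 0.0625 × 110 × 2 / 1.5 = 9.17 and power at N = 110 is 0.851. So 55 per arm reproduces. Dropout: 55 / 0.8 = 68.75, so 69 per arm against the stated 70. The stated size is thus consistent with a model that treats repeated readings as correlated.

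**Two-way ANOVA run literally on independent records.** With total variance σ² and n per arm:

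- Lens main effect: assumed variance σ²/n, true variance (1 + ρ)σ²/n. Type I error = 2[1 − Φ(1.96/√(1 + ρ))].
- Lens-by-time: assumed variance 4σ²/n, true variance 4(1 − ρ)σ²/n. Type I error = 2[1 − Φ(1.96/√(1 − ρ))].
- Lens-by-time power where the mixed model has 85%: Φ(1.960 + 1.036 − 1.960/√(1 − ρ)).

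Figures in brackets are from 20,000 simulated trials at 55 per arm.

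| ρ | Lens main effect, type I | Lens-by-time, type I | Lens-by-time power |
|---|---|---|---|
| 0.3 | 8.6% (8.6%) | 1.9% (2.0%) | 74% |
| 0.5 | 11.0% (11.1%) | 0.56% (0.65%) | 59% |
| 0.7 | 13.3% (13.1%) | 0.035% (0.01%) | 28% |

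The mixed ANOVA held 4.9 to 5.2% for both effects in the same simulations.

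**Both eyes entered as independent records.** The variance of an arm mean is understated by the factor 1 + ICC, where ICC is the inter-eye correlation. Type I error = 2[1 − Φ(1.96/√(1 + ICC))]. With 55 × 2 = 110 eyes per arm, the effective number is 110/(1 + ICC).

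| ICC | Type I error | Effective eyes per arm |
|---|---|---|
| 0.3 | 8.6% | 85 |
| 0.5 | 11.0% | 73 |
| 0.7 | 13.3% | 65 |
| 0.9 | 15.5% | 58 |

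**Lens position.** No arithmetic applies; the sections are set side by side.

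- Section 6.2 excludes previous intraocular surgery, so no implanted lens exists at baseline and no pre-operative tilt, decentration or rotation of it can be recorded.
- Sections 10.3.1 and 10.3.3 limit rotation to the Toric arm, so a lens-by-time model for rotation has neither a second arm nor a first time point. The averaging instruction in 10.3.3 nevertheless names both arms for rotation.
- Tilt and decentration carry no such limit. They lack only the pre-operative value, so a post-operative comparison between arms is possible.
- Section 10.4 defines a subgroup of participants by rotation above 5 degrees, although rotation belongs to a lens. No rule covers a participant with one eye above the threshold and one below, which again shows the unit is unstated.

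**The case against.** A reader might infer that the plan prescribes an ordinary ANOVA that treats pre- and post-operative acuity as independent. The documents do not go that far. Section 10.3 makes time a within-subjects factor for outcome measures, the same cell names a mixed ANOVA, and section 10.1 sizes the trial on repeated measures. Lens by time is a two-factor design, so the acuity sentence may be another name for the same model. That stands. What remains is that one outcome carries two test names and the second omits the repeated factor. Even on the literal reading, the inflated error is in the lens main effect; for the lens-by-time contrast the harm is lost power, not false claims of benefit.

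A reader might also infer that the two eyes will be pooled without a participant term. Nothing says so. The plan speaks of subjects, and one binocular or one-eye value per person would need no inter-eye term. The gap is an unstated unit, and the error rates above apply only if both eyes enter as independent records.

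On lens position, the row supplies its own averages and Bland-Altman analysis, and the ANOVA sentence recurs in every row, which suggests a template. A model that cannot be fitted also produces no wrong result. Both points are fair, but the sentence still covers the row as written. The baseline mark in Appendix 2 is not necessarily an error either: section 3.5 measures rotation partly from the steepest meridian, so it may stand for a reference axis.

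**Conclusion.** The point holds as a set of wording defects in one row of the SAP. The row gives acuity two differently named tests, the plan states no unit of analysis for two-eye data, and the row assigns rotation an analysis that cannot be run. For tilt and decentration the pre/post form of that analysis cannot be run. The instruction to average rotation in both arms conflicts with its Toric-only collection.

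The size is conditional. Roughly 9 to 13% type I error for the lens main effect, and lens-by-time power of 74% down to 28% in place of 85%, require both the literal reading of the acuity sentence and a pre/post correlation of 0.3 to 0.7. Roughly 9 to 16% type I error from two eyes requires that both enter as independent records and an inter-eye correlation of 0.3 to 0.9. None of these correlations is in the documents. Only secondary outcomes are touched; the primary analysis and the sample size are unchanged.

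**What to change.** Rewrite the row as follows.

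- **Acuity:** delete the two-way ANOVA sentence. Use one model comparing arms after second-eye surgery, adjusted for baseline acuity. Visit 2 may stay as a repeated time point.
- **Unit:** use one pre-stated binocular value per person, or both eyes with a participant random effect.
- **Refractive astigmatism:** keep the J0/J45 vector analysis, with the same participant effect if both eyes are used.
- **Tilt and decentration:** compare arms post-operatively only.
- **Rotation:** summarise post-operatively in the Toric arm only, with a participant effect, and remove the monofocal group from the rotation average.
- **Appendix 2:** reconcile the baseline mark for lens orientation, either by deleting it or by stating that it records a reference axis.

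The cost is SAP wording and one line in the schedule. No new data are needed.

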## 4. TRIAL DESIGN

The study is a randomized controlled trial comparing the change of dynamic stability, gaze characteristics, visual function, and quality of life measurements between Toric and non-Toric intraocular lens (IOL) groups.

Vision and balance changes after bilateral implantation of Toric IOLs  
IRAS ID: 286913

The study is a double masked, parallel group design. 140 cataract patients with astigmatism  $>1.0D$  at the Royal Eye Infirmary (REI) of Derriford Hospital will be recruited and randomly assigned to either receive Toric IOLs or non-Toric IOLs for bilateral lens replacement surgery. The randomization will be conducted by the CI who is not involved in the surgical intervention nor the outcome measure assessments. The participants will not know which types of IOLs they are receiving and the study coordinator who assesses the outcome measures will be masked to the types of IOLs given to the participants. Study visits will be carried out before surgery, 3-6 months after first and second eye surgery.

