### **7.3 The randomisation schemes**

The PI will be responsible for recruitment of potential participants from the Cataract clinic at UHP and oversee the consent and eligibility process carried out by the study coordinator. All potential participants will be allocated a unique identification number. The CI, who is independent of the outcome assessments and interventions, will randomize the participants between the intervention and control groups. He will allocate a pseudonymous participant number from 1 to 140. Using simple randomisation with 1:1 allocation ratio through random.org, the 1 to 140 number will be randomly assigned into two groups (Toric IOLs versus non-Toric IOLs). The randomization list will then be passed to the PI, who when recruiting the participants at the pre-surgery clinic can know which type of IOLs (Toric or non-Toric) to prepare for the cataract surgery. At study commencement, each number will be allocated to one of the two groups randomly. This means that subjects are allocated to either arm of the study at the point of recruitment. The randomized list will be held by the PI, who delivers the intervention surgeries. The PI needs to know which lenses are allocated to the patients for surgery purposes but will not participate in the outcome assessment. The study coordinator who is the assessor of the outcome measures will be masked to the allocation of lenses.

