Equation 1: Calculation of J0	$J0 = J \cos 2\alpha$ 
J0 = cylindrical effect at 180° J = cylindrical power a = axis in radians

Equation 2: Calculation of J45	$J45 = J \sin 2\alpha$ 
J45 = cylindrical effect at 45° J = cylindrical power a = axis in radians

Target induced astigmatism (TIA) is the astigmatic correction predicted to occur and will be calculated with Equation 3.

Surgically induced astigmatism (SIA) is the astigmatic correction achieved post-operatively and calculated as Equation 4.

Equation 3: Target induced astigmatism	$TIA = \sqrt{((PreOp J0 - Predicted residual J0)^2 + (PreOp J45 - Predicted residual J45)^2)}$
Equation 4: Surgically induced astigmatism	$SIA = \sqrt{((PreOp J0 - PostOp J0)^2 + (PreOp J45 - PostOp J45)^2)}$

The Correction index (CI) is the ratio of SIA to TIA (Equation 5) and difference vector is the difference between TIA and SIA (Equation 6).

Equation 5: Correction Index	$CI = SIA/TIA$
Equation 6: Difference Vector	$Difference Vector = TIA - SIA$

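### Dependent t-tests are prescribed for the derived astigmatism metrics although the two arms are independent, so the correction index and difference vector have no valid between-lens test

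*Combined protocol and SAP*

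**What the plan says.** The refraction row of the table in section 10.3.3 sends post-operative refractive astigmatism to the Alpins method and then says: "Correlation between SIA and TIA will be assessed, and dependent t-tests will be used to analyse the remaining metrics in the two groups". The equations below the table define the metrics. SIA and TIA are vector magnitudes, "The Correction index (CI) is the ratio of SIA to TIA", and the difference vector is TIA minus SIA (Equations 3 to 6).

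The design is set out elsewhere. Section 4 says "The study is a double masked, parallel group design", with patients "randomly assigned to either receive Toric IOLs or non-Toric IOLs for bilateral lens replacement surgery". Section 7.3 allocates them "Using simple randomisation with 1:1 allocation ratio through random.org" and mentions no matching. Section 10.3 makes lens type the between-participant factor: "The between-subjects factor would be type of IOL lens and the within-subjects factor would be time (pre-surgery vs post-surgery").

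The same table row also contains a general between-group test: "Mixed ANOVA and post-hoc Bonferroni tests will be used to determine the differences between the Toric IOLs group and Monofocal IOLs group". It adds a two-way ANOVA for distance acuity.

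**The concern.** A dependent t-test needs pairs, and the text does not say what is paired with what. Toric and non-Toric participants are different people with no matching, and each person has the same lens type in both eyes, so neither persons nor fellow eyes supply a Toric/non-Toric pair. If the pairing is meant inside each arm, the test is legitimate but answers a different question.

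The hypothesis in section 3.1 is that the Toric lens gives additional correction of astigmatism, which then improves stability. The derived metrics show whether each lens delivered its intended correction. As written, the analyst must either invent a pairing or set two separate within-arm results beside each other, and that choice stays open until the data are in hand.

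**Working it through.** **Inputs.** From section 10.1: 55 per group required, 70 recruited, 20% dropout. From section 10.3: alpha 0.05. From section 10.3.3: Equations 3 to 6. The plan gives no power, effect size or variance for the astigmatism metrics, so the standardised effects below are assumptions.

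**The plan's own figure.** The 55 per group is for the primary outcome. With f = 0.25, N = 110, and two measurements with correlation 0.5 (both assumed, as the plan states neither), the between-factor noncentrality is 0.25² × 110 × 2 / (1 + 0.5) = 9.17 on (1, 108) df, which gives power 0.851. Dropout: 55 / 0.8 = 68.75, so 69 against the stated 70. The figure is reproduced and is used here only as a realistic arm size.

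**Reading 1: pairing across arms.**
- The p-value depends on the order of the list. In one simulated data set of 55 per arm (independent-samples p = 0.23), 20,000 re-orderings of one arm moved the paired p between 0.08 and 0.33. In another (independent p = 0.008) it ran from 0.0004 to 0.030. In neither did it cross 0.05.
- The test needs equal arms. With 70 per arm and each participant completing independently with probability 0.8, the chance of equal completers is Σ P(X = k)² for X ~ Binomial(70, 0.8), which is 0.084. If instead 110 completers are split by coin toss, the chance of 55/55 is C(110, 55)/2¹¹⁰ = 0.076.
- Operating characteristics over 20,000 simulated trials, 55 per arm:

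| True difference | Arbitrary pairs (54 df) | Independent (108 df) |
|---|---|---|
| 0 | 5.2% | 5.1% |
| 0.3 SD | 34.0% | 34.7% |
| 0.5 SD | 72.7% | 73.6% |

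Averaged over trials, arbitrary pairing costs almost nothing. Within one trial, the result is not uniquely defined, and with unequal arms it cannot be computed without discarding participants.

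**Reading 2: pairing within each arm.** SIA and TIA are paired within an eye, so testing whether mean TIA − SIA is zero in one arm is a valid paired test. It yields two separate results and no lens comparison. If the two were then compared by significance, and both arms had the same true effect with power p each, they would disagree with probability 2p(1 − p): 0.50 at p = 0.5 (the maximum), 0.32 at p = 0.8, 0.18 at p = 0.9. Simulation at 0.27 SD and n = 55 gave power 0.501 and disagreement 0.498.

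**Does the mixed ANOVA cover these metrics?** Its within-participant factor contrasts pre-surgery with post-surgery. SIA (Equation 4) is built from pre- and post-operative values together. The correction index (SIA/TIA) and difference vector (TIA − SIA) inherit this. None has a pre-surgery value, so the factor does not exist for them, and the specific sentence names another test in any case.

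**What the correlation shows.** If SIA = 0.5 × TIA exactly, r = 1.00 while the correction index is 0.50. With noise of SD 0.15 D and TIA spread over 1.5 to 4 D (assumed), r = 0.93 and the index is still 0.50. Correlation is not agreement.

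**The case against.** The strongest defence is that the word may be a slip for independent, or that it refers to the valid within-eye test of SIA against TIA. The term for the remaining metrics is not defined, and J0 and J45 do have pre- and post-operative values that can be paired. This stands as far as it goes: a legitimate paired reading exists. It still gives no between-lens result for the correction index or difference vector, and no other sentence supplies one.

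Four stronger readings are tempting, and the documents do not support them.
- *The correlation is the plan's measure of accuracy.* The plan says only that it will be assessed. It also defines the correction index and difference vector, and a lens that under-corrects by a constant fraction would show in the index.
- *Pooling the arms inflates the correlation.* The text does not say that the arms are pooled.
- *The lens comparison on astigmatism as a whole is invalid.* Cylinder and axis are listed in the same row, which has a between-group mixed ANOVA, and acuity has a two-way ANOVA.
- *False positives rise.* The simulation shows no such inflation.

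The disagreement rate of 50% is also a worst case, and the plan never says that lenses will be compared by separate significance tests. Finally, the Alpins metrics are not named among the secondary endpoints in section 3.5 or the table in 3.6.

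**Conclusion.** The point holds for the derived Alpins metrics only. The prescribed test does not fit two independent arms: across arms there are no natural pairs, and within arms the lenses are not compared. The pre/post ANOVA cannot substitute, so the correction index and difference vector have no valid between-lens test.

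Severity is moderate. This is a secondary analysis; the primary outcome and the 110/140 sample size do not change. The harm is an undefined or missing comparison, not a distorted error rate. The textual conflict rests on no assumption. The 8% figure assumes independent dropout at the planned 20%, and the power figures assume standardised normal data with 55 per arm.

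**What to change.** In section 10.3.3, replace the dependent t-tests with a named between-arm comparison for each derived metric, reporting the difference and its 95% confidence interval:
- a Welch t-test on one summary value per participant; or
- if both eyes are analysed, a linear mixed model with lens type as the between-participant factor and a participant random effect.

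State which eyes and which visit are used. Keep the SIA-TIA correlation as a descriptive statistic, reported by arm.

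State also how the correction index will be handled in the non-Toric arm. The documents do not give the predicted residual for that lens. If it is close to the pre-operative astigmatism (an assumption), TIA by Equation 3 is near zero. The ratio is then unstable on any scale, since halving TIA doubles the index for the same SIA. In that case, base the between-arm comparison on the difference between SIA and TIA and report the index descriptively.

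The cost is a few sentences of analysis-plan wording, agreed before outcome data are seen. No extra data or participants are needed.
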